	
 • To evaluate pharmacokinetic parameters of PBTZ169, capsules 40 mg, after multiple administration under fasting conditions at doses that will be defined according to the results of the analysis of the drug's tolerance, safety and pharmacokinetics after single administration in healthy volunteers, i.e.: maximum concentrations C_{max} and $C_{max,ss}$, trough concentration after multiple administration C_{trough}, time to maximum concentration T_{max} and $T_{max,ss}$, areas under the curve AUC_{0-t}, $AUC_{0-\infty}$ and AUC_{ss}, half-life $T_{1/2}$, mean retention time MRT, total clearance Cl_t, distribution volume V_d and V_{ss}, elimination constant k_{el}.  To evaluate the elimination kinetics of PBTZ169, capsules 40 mg, in urine (renal clearance Cl_{ren}) in healthy volunteers after single administration under fasting condition at rising doses (40 mg, 80 mg, 160 mg, 320 mg, 640 mg) and multiple administration under fasting conditions at doses that will be defined according to the results of the analysis of the drug's tolerance, safety and pharmacokinetics after single administration.
Planned number of the study centers and their location	At the territory of the RF, the participation of 3 study centers is planned

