Before the volunteers will be included into Cohort 2, the drug pharmacokinetic results will have been received for Cohort 1. Time points for blood and urine sampling can be adjusted for all successive cohorts based on the data concerning pharmacokinetics and safety of administration of PBTZ169 capsules 40 mg.

Screening of volunteers into each successive cohort can be started not earlier than 24 h after all the volunteers from the previous cohort have received the drug. The subjects will be randomized within the cohort after volunteers from previous cohort have received the drug. The volunteers of each successive cohort will administer single dose of the drug minimum 7 days after the volunteers from the previous cohort have received the drug if dose-limited toxicity (DLT) is found in less than 50% volunteers from the group. For Cohort 1, DLT reported in 2 volunteers from the first three patients will be considered as achievement of this criterion and will result in the study termination, thus, the successive three subjects will not be included into the study. In this study, DLT will include any class 3 and more toxicity according to Toxicity Grading Scale for Healthy Adult and Adolescent Volunteers Enrolled in Preventive Vaccine Clinical Trials which is "possibly", "probably" and "definitely" related with the administration of PBTZ169.

The volunteers from each group will be admitted to hospital in the evening before dosing.

Back-ups from cohorts C1-C5 will be admitted to hospital simultaneously with the main volunteers of the cohorts for not more than 24 h and will be discharged and complete the study participation

if their participation is not necessary. If back-up is necessary in any cohort, the period of hospitalization and all the study procedures for respective back-up will be equivalent to those for substituted volunteer. In Cohort 1, back-up will be hospitalized with the second three volunteers.

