Each healthy volunteer from the main groups of cohorts C1-C5 will receive only one dose of the test drug in the morning under fasting conditions (10 h of night fasting) with 300 mL of bottled water. On the day of administration, water intake is ad libitum, except for 1 h within the drug administration during which water intake is prohibited and for 4 h after the drug administration (water intake is prohibited during the first hour, water intake will be limited by 100 mL of bottled water ever hour for the successive 3 h). Food intake will be prohibited for 4 h after the drug administration.

Volunteers from cohorts C1 and C2 will have their venous blood samples taken to determine PBTZ169 concentration before the drug administration: -5 min, 0 min, afterwards at the following time points after the drug administration: in 0:10, 0:20, 0:30, 0:45, 1:00, 1:30, 2:00, 2:30, 3:00, 3:30, 4:00, 5:00, 6:00, 8:00, 10:00, 12:00 and 24:00 (h:min).

Volunteers from Cohort 3 will have their venous blood samples taken to determine PBTZ169 concentration before the drug administration: -5 min, 0 min, afterwards at the following time points after the drug administration: in 0:10, 0:20, 0:30, 0:45, 1:00, 1:30, 2:00, 2:30, 3:00, 3:30, 4:00, 5:00, 6:00, 8:00, 10:00, 12:00, 48:00 (h:min).

Volunteers from Cohort 4 will have their venous blood samples taken to determine PBTZ169 concentration before the drug administration: -5 min, 0 min, afterwards at the following time points after the drug administration: in 0:10, 0:20, 0:30, 0:45, 1:00, 1:30, 2:00, 3:00, 4:00, 5:00, 6:00, 8:00, 10:00, 12:00, 24:00 and 48:00 (h:min).

Volunteers from Cohort 5 will have their venous blood samples taken to determine PBTZ169 concentration before the drug administration: -5 min, 0 min, afterwards at the following time points after the drug administration: in 0:10, 0:20, 0:30, 0:45, 1:00, 1:30, 2:00, 3:00, 4:00, 5:00, 6:00, 8:00, 10:00, 12:00, 24:00, 48:00 and 72:00 (h:min).

At every time point of blood sampling for PBTZ169 concentration determination, additional venous blood will be also sampled for further storage of samples for possible determination of additional parameters. Additional blood can be sampled to control the current parameters to assure safety of volunteers.

Urine will be sampled from every volunteer in each of cohorts during the first 24 hours after dosing within the the following time

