periods: 0–2, 2–6, 6–12 and 12–24 h to evaluate pharmacokinetics. 12–24 h urine samples will be analyzed only at non-zero concentration of PBTZ169 in 6–12 h sample.

During the whole period of blood sampling for pharmacokinetics after the drug administration, the volunteers will be at hospital and will be discharged after all procedures planned in the protocol have been finished, afterwards the monitoring will be continued under out-patient conditions.

Thus, total in-patient period for every cohort will be as follows:

- C1 and C2 - 3 days (including the admission day, day of the test drug administration and 24 h after the drug administration)
- C3 and C4 - 4 days (including the admission day, day of the test drug administration and 48 h after the drug administration)
- C5 - 5 days (including the admission day, day of the test drug administration and 72 h after the test drug administration).

After the discharge from hospital, volunteers from C1–C5 should visit the study center in 5±1 days after the drug administration for follow-up procedures (safety evaluation).

14±1 days after the drug administration, the last visit (Visit 3) will take place in the form of phone contact after which the volunteers will finish the study participation. Thus, total follow-up period will be 14 days after the drug administration for each volunteer.

After the last volunteer from those enrolled in the cohorts of Stage 1 completes the study, safety and pharmacokinetics will be analyzed using the data of all cohorts of a single dose study. Upon the termination of an analysis of the data obtained during the Stage I, an independent Committee for data evaluation and study subjects' safety will be called. The results of the session of the Committee dedicated to the discussion of the data obtained in the first 5 cohorts (the results of the statistical analysis) will serve for preparing a resolution about the safety, tolerance and pharmacokinetics of the drug taken once in the first 5 cohorts. Takin into account the resolution of the independent Committee about the data evaluation and the safety of study subjects, the Sponsor will:

- *Determine the doses of PBTZ-169 for multiple administration during the Stage 2 of the study;*
- *Take the decision on the necessity to adjust blood and urine sampling timepoints ;*
- *Take the decision about the necessity of a study procedure correction.*

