	
concentration determination, additional venous blood will be also sampled for further storage of samples for possible determination of additional parameters.
 
Urine will be sampled from every volunteer in each of cohorts during the first 24 hours after the first and last dosing within the the following time periods: 0–2, 2–6, 6–12 and 12–24 h to evaluate pharmacokinetics. 12-24 h urine samples will be analyzed only at non-zero concentration of PBTZ169 in 6-12 h sample.
 
During the whole period of PBTZ169 administration, the volunteers will be monitored in the hospital; afterwards the monitoring will be continued under outpatient conditions. Total follow-up period will be 14 days after the last drug dose administration for each volunteer.
 
After the discharge from the hospital, volunteers from cohorts C6-C7 should visit the study center in 1 and 2 days for blood sampling at 48 h and 72 h time points and in 7 ± 1 days and 14 ± 1 days for the last drug dosing (the study Day 19 ± 1 and Day 28 ± 1) for follow up procedures (safety evaluation).
 
21 ± 1 days after the last drug dosing (the study Day 35 ± 1) in volunteers from cohorts C6-C7, final visit will be performed in the form of phone contact after which the volunteers will finish the study participation.
 
For patients, who will receive multiple dosing, hospitalization period will be 16 days (including admission day, 14 days of the test drug administration and 24 h of patient monitoring under inpatient conditions after last drug dosing).
 
The results obtained in this study will be used to plan subsequent safety and efficacy clinical studies of PBTZ169.

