	
processing will be performed on this population.
 
Safety parameters evaluation
 
Safety evaluation will include determination of AE/SAE, vital signs, ECG data, physical examination and laboratory analyses in the safety population.
 
All the safety parameters will be performed using descriptive statistics parameters (mean, standard deviation, median, minimum and maximum, range, quartiles, number of valid cases - for quantitative variables; absolute count, ratio, distribution - for qualitative variables).
 
Pharmacokinetic parameters
 
Pharmacokinetic parameters will be determined using WinNonlin software (Phoenix Inc) by the results of the drug concentration measurement. Individual pharmacokinetic curves will be plotted with determination of all calculable parameters and descriptive statistics parameters.

--	--

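### Assay of the 12–24 h urine depends on a 6–12 h concentration, so a dilute 6–12 h sample can leave measurable late excretion unassayed; the size depends on half-life, assay limit and how renal clearance is calculated

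*Combined protocol and SAP*

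**What the plan says.** All references are to section 1, Study Summary.

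- **Study tasks.** One task is "To evaluate the elimination kinetics of PBTZ169, capsules 40 mg, in urine", expressed as renal clearance, at every single dose from 40 to 640 mg and after multiple dosing. Renal clearance is also a listed parameter for both stages.
- **Design and methodology, Stage 1.** Urine is collected over "periods: 0–2, 2–6, 6–12 and 12–24 h to evaluate pharmacokinetics". The rule is then "12–24 h urine samples will be analyzed only at non-zero concentration of PBTZ169 in 6–12 h sample".
- **Design and methodology, Stage 2.** The same intervals apply after the first and last doses, with the same condition: "12-24 h urine samples will be analyzed only at non-zero concentration of PBTZ169 in 6-12 h sample".
- **Water, Stage 1.** "On the day of administration, water intake is ad libitum, except for 1 h within the drug administration" and except for the 4 h after dosing. In those 4 h water is barred for the first hour and capped at 100 mL per hour for the next three.
- **Statistical methods.** "Pharmacokinetic parameters will be determined using WinNonlin software (Phoenix Inc) by the results of the drug concentration measurement". No renal clearance formula or interval is given. There is no rule for urine that is below the assay limit or not assayed, and non-zero is not tied to an assay limit.

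**The concern.** The rule takes a zero concentration at 6–12 h to mean that nothing worth measuring follows. Renal clearance is built from amount, which is concentration times volume. At a given excretion rate, concentration falls as urine flow rises. In Stage 1, drinking is free after 4 h, so the 6–12 h urine can be dilute. Dosing is in the morning, so the 12–24 h collection takes in the night and may be more concentrated. A 6–12 h result below the assay limit therefore does not show that excretion has ended.

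At stake is the 0–24 h amount excreted and, depending on the calculation, renal clearance itself. If one assay limit serves all cohorts, urine from the lowest doses lies nearest to it, so any loss would fall mainly there.

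**Working it through.** **Inputs.** From the documents: the four urine intervals, the conditional assay, and the cohort sizes. Not in the documents, hence assumed: first-order absorption and elimination, absorption rate ka = 1.5 per h, half-life 3 to 30 h, and 12–24 h urine flow either equal to 6–12 h flow or half of it. The plan states no figure to reproduce.

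**Step 1: excretion shares.** With constant renal clearance, the amount excreted to time t is proportional to

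A(t) = [ka/(ka − k)] × [(1 − e^(−kt))/k − (1 − e^(−ka·t))/ka], with k = ln 2 / half-life.

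Example, half-life 12 h: k = 0.0578, A(6) = 4.58, A(12) = 8.31, A(24) = 12.81. The 12–24 h share is (12.81 − 8.31)/12.81 = 35%. The 6–12 h share is (8.31 − 4.58)/12.81 = 29%.

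**Step 2: can the later sample be the more concentrated one?** The ratio of mean excretion rates, late to early, is (12–24 h share/12)/(6–12 h share/6). At 12 h this is (0.351/12)/(0.291/6) = 0.60. It equals the concentration ratio at equal flow, and doubles if 6–12 h flow is twice the later flow. Its reciprocal is the flow ratio above which the later sample is the more concentrated.

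| Half-life | 6–12 h share | 12–24 h share | Concentration ratio, equal flow | Ratio, two-fold flow | Flow ratio needed |
|---|---|---|---|---|---|
| 3 h | 22% | 7% | 0.16 | 0.31 | 6.4 |
| 6 h | 29% | 22% | 0.38 | 0.75 | 2.7 |
| 12 h | 29% | 35% | 0.60 | 1.21 | 1.7 |
| 20 h | 28% | 41% | 0.74 | 1.47 | 1.4 |
| 30 h | 27% | 45% | 0.81 | 1.63 | 1.2 |

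**Step 3: effect on one volunteer's renal clearance.** Suppose the 6–12 h result is below the limit and set to zero, and the amount is divided by AUC0-24.

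- 12–24 h sample assayed and measurable: ratio to truth = 1 − (6–12 h share).
- 12–24 h sample unassayed and counted as zero: ratio to truth = 1 − (6–12 h share) − (12–24 h share).

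At half-lives of 6, 12 and 20 h this gives 0.71, 0.71 and 0.72 with assay, against 0.49, 0.36 and 0.30 without.

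With matched intervals ending at the last measurable urine (here Ae0-6/AUC0-6), the ratio is 1 in either case under constant renal clearance.

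**Step 4: how often.** A simulation used urine-flow CV 50%, independent between the two intervals. The table shows the chance that a measurable 12–24 h sample goes unassayed, by the median 6–12 h concentration as a multiple of the assay limit.

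| Half-life | Equal median flow, 1× / 2× | Two-fold flow, 1× / 2× | Either, 4× |
|---|---|---|---|
| 3 h | about 0% / 0% | about 0% / 1% | about 0% |
| 6 h | 1% / 2% | 13% / 6% | about 0% |
| 12 h | 7% / 5% | 33% / 7% | about 0% |
| 20 h | 13% / 6% | 40% / 7% | about 0% |

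The mean loss in renal clearance due to the rule, with unassayed urine counted as zero, is this chance times the 12–24 h share. At equal median flow it is at most about 0.13 × 0.41 = 0.05 of the true value. In the worst two-fold case it is 0.40 × 0.41 = 0.16.

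**The case against.** The strongest case against is that bias is not shown.

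- **No stated calculation counts unassayed urine as zero.** The text available is a summary, so a missing formula there is weak evidence of a bad one. With matched intervals the rule introduces no systematic error. This stands, and it makes the bias conditional.
- **The harm needs several things at once:** concentrations near the limit, a fairly long half-life and more dilute urine at 6–12 h. This stands. At a 3 h half-life, or at four times the limit, the effect is close to nil.
- **Much of the low-dose loss comes from the 6–12 h sample itself.** If that sample is set to zero, 22–29% of 0–24 h excretion goes with or without the rule. This stands. The rule adds to that loss and does not cause it.
- **The plan can adapt.** "Time points for blood and urine sampling can be adjusted for all successive cohorts", and study procedures can be corrected after Stage 1. This stands in part: the flexibility is there, but nothing commits the sponsor to revisit the assay condition.
- **The dilution argument is weaker for Stage 2**, where water is capped after dosing and no free-intake wording appears. This stands for the water regime. The logical fault in using concentration to decide on assay remains.

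A reader might infer a spurious rise in renal clearance with dose, or from first to last dose in Stage 2. The first is possible only if one assay limit applies and unassayed urine counts as zero. The second is weak, because Justification of dose selection presumes the two highest tolerated single doses for Stage 2, where a zero at 6–12 h is least likely.

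**Conclusion.** The assay condition is unsound in principle and cheap to remove, but its harm is conditional. It can leave a measurable 12–24 h sample unassayed when 6–12 h concentrations lie near the assay limit and the half-life is about 6–12 h or longer. The share of 0–24 h excretion at risk is about 7% at a 3 h half-life, rising to 45% at 30 h, under the assumed kinetics. Renal clearance is biased downward only if the unassayed amount is counted as zero against AUC0-24 or longer. Otherwise the cost is precision and an incomplete 0–24 h amount.

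A reader might infer that the rule always biases renal clearance downward, or that it costs a fixed share such as 40%. The documents support neither. They fix no renal clearance calculation, and 40% would need a half-life of roughly 20 h, which they do not give.

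**What to change.** Delete the condition in the Stage 1 and Stage 2 urine-sampling text, and assay every collected 12–24 h sample.

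If the condition is kept:

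- define non-zero against the assay limit;
- calculate renal clearance over matched urine and plasma intervals ending at the last assayed interval with measurable drug, for example Ae0-6/AUC0-6 (a 6 h plasma point is listed for every cohort);
- do not count unassayed urine as zero.

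In either case, state how a below-limit 6–12 h sample is handled, since deleting the condition does not settle that. Cohort 3's listed plasma times run from 12 h to 48 h with no 24 h point, so AUC0-24 there would need interpolation.

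**Cost.** For planned main-group volunteers, at most 5 × 6 = 30 assays in Stage 1 and 2 cohorts × 6 × 2 doses = 24 in Stage 2, so 54 in all; some of these would be run anyway. A third Stage 2 cohort, which the Stage 2 text allows, would add 6 × 2 = 12, and replacements somewhat more. No extra urine is collected.

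### Stage 1 in-patient observation lengthens with dose (24, 48, 72 h), and the summary gives adverse events no common onset window, so part of any dose trend could reflect closer observation; the likely size is modest

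*Combined protocol and SAP*

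**What the plan says.** All references are to the Combined protocol and SAP, section 1, Study Summary.

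**In-patient stay (Design and methodology, Stage 1).** It is set by cohort:
- 40 and 80 mg: "C1 and C2 - 3 days (including the admission day, day of the test drug administration and 24 h after the drug administration".
- 160 and 320 mg: "C3 and C4 - 4 days (including the admission day, day of the test drug administration and 48 h after the drug administration".
- 640 mg: "C5 - 5 days (including the admission day, day of the test drug administration and 72 h after the test drug administration".

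The stay follows the pharmacokinetic sampling schedule, which is longer at the higher doses.

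**After discharge.** The scheme is the same for all five cohorts: "afterwards the monitoring will be continued under out-patient conditions". Volunteers "should visit the study center in 5±1 days after the drug administration for follow-up procedures (safety evaluation", and there is a final phone contact at day 14±1. The text states that "total follow-up period will be 14 days after the drug administration for each volunteer".

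**Analysis.** Under Statistical methods, safety is descriptive. Qualitative variables are given as "absolute count, ratio, distribution - for qualitative variables", so proportions are planned as well as counts. No onset window and no split between in-patient and out-patient events is described. The Reference drug row reads not applicable.

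**Use.** After Stage 1, "safety and pharmacokinetics will be analyzed using the data of all cohorts of a single dose study". An independent committee considers these results, and the sponsor then sets the Stage 2 doses.

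**The concern.** Between 24 h and 72 h after dosing, a 640 mg volunteer is in hospital and a 40 or 80 mg volunteer is at home, with the next planned contact at day 5±1. If staff in hospital notice or elicit more minor events than are reported later, detection in that interval rises in step with dose. With no reference arm, nothing in the trial shows the background rate under hospital observation.

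A pooled table by cohort cannot separate the two explanations, and it can mislead in either direction. Background events could look like a dose trend. A real signal at 24-72 h at the top dose could also be explained away as closer observation. The exposed use is the cross-cohort safety summary that the committee reads before Stage 2 doses are set.

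Time at risk is equal, at 14 days for everyone. What differs is how closely that time is watched. Proportions, or rates per person-day over 14 days, would therefore not remove the difference.

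**Working it through.** **1. Reproduce the plan's figures.** Admission day + dosing day + (post-dose hours ÷ 24):
- C1-C2: 1 + 1 + 1 = 3 days.
- C3-C4: 1 + 1 + 2 = 4 days.
- C5: 1 + 1 + 3 = 5 days.

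All three match. As a share of the 14 days (336 h), in-patient time is 24/336 = 7.1%, 48/336 = 14.3% and 72/336 = 21.4%.

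**2. Model for a difference in detection alone.** The documents give neither a background event rate nor a detection rate, so both are assumed. Take a constant background rate unrelated to dose, full detection during the d in-patient days after dosing (d = 1, 2, 3), and detection at a fraction q of that afterwards. Detected events per volunteer over 14 days are proportional to d + (14 − d)q.

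| q (assumed) | C1-C2, d = 1 | C3-C4, d = 2 | C5, d = 3 | C3-C4 : C1-C2 | C5 : C1-C2 |
|---|---|---|---|---|---|
| 0.7 | 1 + 9.1 = 10.1 | 2 + 8.4 = 10.4 | 3 + 7.7 = 10.7 | 1.03 | 1.06 |
| 0.5 | 1 + 6.5 = 7.5 | 2 + 6.0 = 8.0 | 3 + 5.5 = 8.5 | 1.07 | 1.13 |
| 0.3 | 1 + 3.9 = 4.9 | 2 + 3.6 = 5.6 | 3 + 3.3 = 6.3 | 1.14 | 1.29 |

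The limits are 1.00 at q = 1 and 3.00 at q = 0, where nothing is detected after discharge. At q = 0.2 the C5 ratio is 5.2/3.6 = 1.44.

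**3. Where the difference sits.** C5 minus C1 is (3 + 11q) − (1 + 13q) = 2(1 − q). All of it comes from the two days between 24 h and 72 h.

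**4. Size in volunteers.** Assume 0.05 events per volunteer-day and q = 0.5. The chance of at least one detected event is 1 − exp(−0.05 × 7.5) = 0.313 in C1-C2, 1 − exp(−0.05 × 8.0) = 0.330 in C3-C4 and 1 − exp(−0.05 × 8.5) = 0.346 in C5. Out of six, that is 1.88, 1.98 and 2.08 volunteers expected with an event.

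From exact binomials with six per cohort, the C5 count exceeds the C1 count with probability 0.43 and falls below it with probability 0.33. With equal detection (q = 1) each is 0.39. At q = 0.2 the expected numbers in C1-C2 and C5 are 0.99 and 1.37, and the two probabilities are 0.46 and 0.25.

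**5. Which windows are matched.**
- Onset at 0-24 h is in-patient in every cohort, so the ratio there is 1.00 by construction.
- The day 5±1 visit (days 4-6) falls 3-5 days after discharge in C1-C2, 2-4 days in C3-C4 and 1-3 days in C5. Events recalled at that visit are therefore not equally ascertained. Findings measured at the visit are.

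**The case against.** The best case for the plan has five parts.

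- **Follow-up is otherwise identical.** Every cohort has 14 days, the same clinic visit, the same call and continued out-patient monitoring. This stands. A reader might infer unequal follow-up or unequal time at risk from the 24/48/72 h stays, and the text rules that out.
- **Proportions are planned.** A reader might take the plan to use raw counts only, but it lists ratio and distribution too. This stands as a correction of that reading. It does not remove the detection difference.
- **The effect is small.** Over days 0-3 alone, the same model gives C5:C1 ratios of 3/2.4 = 1.25, 3/2 = 1.50 and 3/1.6 = 1.88 for q = 0.7, 0.5 and 0.3. Quoting these as the size would overstate it, because no planned table is described for that window. Against the stated 14-day follow-up, 1.06 to 1.29 is the fair range. The model also applies one flat detection rate after discharge, so it gives no extra credit for events still present at the day 5±1 visit.
- **The decision rules are within-cohort.** Escalation depends on related toxicity of class 3 or higher in under half of a cohort. Stage 2 doses rest on good tolerance of the corresponding single dose, including that same criterion. A reader might infer that escalation is biased, but nothing in the documents shows this. The study is described as non-comparative, and closer observation would tend to overstate high-dose toxicity, not hide it.
- **Only the summary is available.** A fuller adverse-event section might define windows, and how events are elicited in each setting is not described. This limits confidence.

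What remains is that the committee will read the five cohorts side by side, and the described summary cannot show how much of a gradient comes from the setting.

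**Conclusion.** The concern holds in a limited form. In-patient observation after dosing is aligned with dose, no common onset window or split by setting is described, and there is no reference arm. Part of any rise in adverse events with dose could therefore reflect closer observation between 24 h and 72 h.

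The expected distortion over 14 days is 6% to 29% for 640 mg against 40 mg, if out-patient detection is 70% to 30% of in-patient detection and the drug has no effect. With six volunteers per cohort, a shift of that size is hard to tell from chance. The direction requires only that out-patient detection is lower than in-patient detection. The size rests wholly on assumed rates.

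The documents do not support a claim that the dose-limiting toxicity rule or the Stage 2 dose choice is compromised. This is a cheap improvement to the analysis, not an error that undermines the trial. Confidence is medium, because only the summary could be read.

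**What to change.** In the Stage 1 safety analysis:

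1. Base the descriptive comparison across doses on events with onset at 0-24 h, when all five cohorts are in hospital.
2. Show events with onset at 24-72 h in a separate table by setting (in-patient or out-patient), with each cohort's in-patient hours stated.
3. Assign events recalled at the day 5±1 visit or the day 14±1 call to a window by onset date. Treat only findings measured at the day 5±1 visit as comparable across cohorts.
4. Keep the all-events table and listing.

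**Cost.** This needs a few lines of analysis text and one more table, with no change to visits, stays or dosing. It assumes that onset dates, and times around the 24 h and 72 h boundaries, are recorded; the summary does not say.

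**Downside.** Counts will be small. At the assumed 0.05 events per volunteer-day, 6 × (1 − exp(−0.05)) = 0.29 volunteers per cohort would have a background event in the first 24 h. That window also misses later events, so it must be read beside the 24-72 h table and the all-events table.

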The drug administration in Cohort 7 can be started not earlier than 7 days after all the volunteers from the previous cohort administer the last drug dose if DLT is reported in less than 50% volunteers from the previous cohort before the latest volunteer is discharged from the hospital. DLT will include any class 3 and more toxicity according to Toxicity Grading Scale for Healthy Adult and Adolescent Volunteers Enrolled in Preventive Vaccine Clinical Trials which is "possibly", "probably" and "definitely" related with the

administration of PBTZ169.

Volunteers included in cohorts C6-C7 are hospitalized in the evening on Day 0 before the first drug dose administration. In the evening of Day 1, every healthy volunteer will take the first dose of the test drug under fasting condition (10 h of night fasting) with 300 mL of bottled water. Afterwards the volunteers will continue daily administration of the test drug at constant dose (depending on the cohort) under in-patient conditions. The drug will be administered daily under fasting condition (10 h of night fasting) o.d. in the morning at the same time \pm 15 and always with 300 mL of bottled water. Food intake is prohibited for the volunteers during 4 hours after the first, 7th and last (14th) dose of the test drug; water intake will be also regulated during this time: not more than 100 mL of bottled water per hour. On the days of the rest drug administrations, the volunteers are prohibited to take food for 2 h after the drug administration; water intake will be also regulated during this time: not more than 100 mL of bottled water per hour. The drug administration period will be 14 days.

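### The DLT count that decides whether Cohort 7 may be dosed closes at Cohort 6 discharge (scheduled Day 15), six days before Cohort 7 can start (Day 21)

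*Combined protocol and SAP*

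**What the plan says.** All references are to the combined protocol and SAP, section 1 Study summary, row Design and methodology, unless stated otherwise.

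- **Stage 2 escalation rule, timing.** Cohort 7 dosing "can be started not earlier than 7 days after all the volunteers from the previous cohort administer the last drug dose".
- **Stage 2 escalation rule, toxicity.** The same sentence makes escalation conditional on the Cohort 6 count: it is allowed "if DLT is reported in less than 50% volunteers from the previous cohort before the latest volunteer is discharged from the hospital". A DLT is a class 3 or higher toxicity at least possibly related to PBTZ169.
- **Stage 2 inpatient stay.** The length is fixed in these words: "hospitalization period will be 16 days (including admission day, 14 days of the test drug administration and 24 h of patient monitoring". Once it ends, "afterwards the monitoring will be continued under outpatient conditions".
- **Stage 2 follow-up.** Volunteers return for blood sampling at 48 h and 72 h. The two safety visits are timed at "7 ± 1 days and 14 ± 1 days for the last drug dosing (the study Day 19 ± 1"; the second is printed as Day 28 ± 1. The closing phone contact is timed at "21 ± 1 days after the last drug dosing (the study Day 35 ± 1".
- **Stage 1, for comparison.** The next cohort is dosed "minimum 7 days after the volunteers from the previous cohort have received the drug", with the same 50% threshold and no discharge cut-off. Stage 1 volunteers "should visit the study center in 5±1 days after the drug administration for follow-up procedures (safety evaluation".

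**The concern.** The sentence that imposes a 7-day wait also stops counting DLTs about one day into it. For the criterion as written, the rest of the wait adds nothing.

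This is a first-in-human study whose main tasks are safety and tolerance. Justification of dose selection presumes that the two highest well-tolerated single doses will be taken into multiple dosing. If all five single doses are tolerated, those are 320 mg and then 640 mg daily for 14 days, so this rule would guard a doubling of the daily dose.

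The Stage 1 rule has no such cut-off. After 14 daily doses, the explicit counting window is therefore narrower than the one used after a single dose.

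**Working it through.** **Calendar for one Cohort 6 volunteer**

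- Admission is on Day 0 and the first dose on Day 1. The text gives both evening and morning for the first dose, but this does not change the day.
- Fourteen daily doses put the last on Day 1 + 13 = Day 14.
- Discharge follows 24 h later, on Day 15. Days 0 to 15 inclusive make 16 days, which reproduces the stated stay.
- The earliest Cohort 7 dose is Day 14 + 7 = Day 21, counted from the last-dosed volunteer.
- The uncounted interval is 21 − 15 = 6 days.

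**Where the safety visit falls**

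- Stage 1: 5 ± 1 days is 4 to 6 days after dosing, always inside the 7-day wait.
- Stage 2 by interval: 14 + (7 ± 1) = Days 20 to 22, which can fall after Cohort 7's first dose.
- Stage 2 by printed day: Day 19 ± 1 = Days 18 to 20, always before it.
- The later contacts agree with their printed days (14 + 14 = 28; 14 + 21 = 35). Day 19 equals 14 + 5, the Stage 1 interval. The text does not show which figure is meant.

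**Stopping count**

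With six volunteers, fewer than 50% means at most 2, so 3 of 6 blocks escalation. Two by discharge is 2/6 = 33% and passes. A third on Day 18 makes 3/6 = 50% but is not counted.

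**Size, under assumed rates**

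Let p be a volunteer's total DLT risk by Day 21 and f the share of DLTs first reported after the cut-off. Volunteers are taken as independent.

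- Full count: P(proceed) = P(X ≤ 2), X ~ Bin(6, p).
- Count closed at discharge, all six exposed to the gap: the same with p(1 − f) in place of p.

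Worked case, p = 0.30 and f = 0.10:

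- Full count: 0.1176 + 0.3025 + 0.3241 = 0.744.
- Closed at discharge (risk 0.27): 0.1513 + 0.3358 + 0.3105 = 0.798.
- Difference: 5.3 percentage points. This is the probability of at most 2 DLTs by discharge but at least 3 by Day 21.

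The cut-off is the latest volunteer's discharge, so volunteers who finished earlier are counted for longer. Simultaneous dosing is stated only for Stage 1, and three centres are planned. The table therefore also shows three exposed or one exposed, with the others at full risk p. All rows use f = 0.10.

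| p | Full count | Closed at discharge, six exposed | Rise in points: six exposed | Three exposed | One exposed |
|---|---|---|---|---|---|
| 0.10 | 98.4% | 98.8% | 0.4 | 0.2 | 0.07 |
| 0.20 | 90.1% | 92.4% | 2.3 | 1.2 | 0.4 |
| 0.30 | 74.4% | 79.8% | 5.3 | 2.7 | 0.9 |
| 0.40 | 54.4% | 62.7% | 8.3 | 4.1 | 1.4 |
| 0.50 | 34.4% | 44.2% | 9.8 | 4.8 | 1.6 |

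At p = 0.30 with six exposed, the rise is 2.7 points if f = 5% and 10.2 points if f = 20%.

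**The case against.** The clause is a minimum condition for escalation and does not oblige anyone to escalate. Volunteers are still seen in the uncounted days: they attend at 48 h and 72 h (Days 16 and 17), outpatient monitoring continues, and Withdrawal criteria allow the sponsor or investigator to terminate the study. The gap is thus in the count and not in surveillance. That is correct, but acting on a late event would be discretionary. The 48 h and 72 h visits are listed for blood sampling only. The independent Committee is described as meeting on Stage 1 data, and no review between Cohorts 6 and 7 is described.

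The effect may also be small. Stage 2 doses must first have been well tolerated as single doses, so the 10% row may be as relevant as the higher ones, although 14 daily doses may raise the risk. A replacement volunteer dosed later would delay the latest discharge and bring some or all of the others' gap into the count. Most of the rule's leniency comes from the 50% threshold itself. These points stand, and they limit the size.

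The visit-date conflict is a separate inconsistency and the gap does not depend on it. It matters here because that visit is the natural source of the missing data. Finally, extending the count to the first Cohort 7 dose still leaves out Cohort 6 events reported after that dose, for example at the Day 28 visit. That also stands.

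**Conclusion.** The concern holds. On the planned schedule the count closes on Day 15, Cohort 7 can start on Day 21, and nothing in the study summary, the only text available for review, brings a DLT first reported in between into the rule. Escalation at 3 of 6 is therefore permitted as written. This conclusion needs no assumed rate.

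The practical size cannot be determined from the documents. With 10% of DLTs late and all six volunteers exposed, the added chance of proceeding runs from 0.4 points at 10% risk to 9.8 points at 50%. It is about half that with three exposed and at most 1.6 points with one. These figures rest on assumed risks, independent volunteers and exactly six in the cohort. The point should be fixed because it is a gap in a written safety rule that wording can close.

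**What to change.** 1. In the Stage 2 escalation rule, end the DLT count at the first dose in Cohort 7 instead of at the latest volunteer's discharge.
2. In the Stage 2 follow-up text, settle the first safety visit as either 7 ± 1 days after the last dose (Day 21 ± 1) or 5 ± 1 days (Day 19 ± 1, the Stage 1 interval).
3. In either case, require that visit to be completed and reviewed for all Cohort 6 volunteers before Cohort 7 is dosed.

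**Cost.** The change is protocol wording. At Day 19 ± 1 the visit ends by Day 20, so only the review could add time. At Day 21 ± 1 the delay is up to 1 day plus the review. Cohort 7 screening may start on Day 15 and must fall within 10 days of dosing, so it lasts to Day 15 + 10 = Day 25. That leaves 25 − 21 = 4 days of slack without re-screening. A low-risk dose is rarely blocked: at an assumed 10% risk with 10% late, the chance of proceeding falls only from 98.8% to 98.4%. The change does not alter the 50% threshold.
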